**Aim 1. Demonstrate the feasibility of stroke subject recruitment and retainment.** Our pilot power analysis determined that at least 40 stroke patients will be needed in a full R01 trial. We **hypothesize** that our experimental site at the OUHSC campus has the full ability to recruit 12 eligible patients in one year and retain most of them to complete this trial (detailed in Aim 2).

**Aim 2. Determine the effect of the targeted HD-tDCS on reducing the upper limb motor impairment.** We hypothesize that: 1) facilitating the ipsilesional primary motor cortex will improve the function of the damaged corticospinal tract and therefore, reduce upper limb muscle synergies. 2) inhibiting the contralateral premotor cortex will reduce the maladaptive use of the cortico-reticulospinal tract and thus, also reduce impairment. This randomized, double-blinded, sham-controlled cross-over study will include the anodal HD-tDCS targeting the **ipsilesional primary motor cortex (Aim 2a)**, and the cathodal HD-tDCS over the **contralateral premotor cortex (Aim 2b)**, compared to sham stimulation. We will use a subset of Fugl-Meyer Upper Extremity assessment which is mainly related to the muscle synergies as the primary outcome measure. The TMS-induced motor-evoked potentials (MEP) will be measured to determine the use of ipsilesional corticospinal tract and the contralateral cortico-reticulospinal tract, with the MEP latency as the secondary outcome measure. Resting-state EEG will also be obtained to have the *brain symmetry index* as the third outcome measure for evaluating the acute effect of HD-tDCS on brain plasticity.

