**Assessments and Outcome Measures.** The following assessments will be performed for baseline, pre- and (immediate) post-intervention time frames. The Fugl-Meyer-Upper Extremity (FM-UE) assessment Part A - mainly related to the muscle synergies and serves as the primary outcome measure. This subset FM-UE assessment increases the sensitivity of the measure and reduces the test time from 30 mins (full assessment) to 10 mins. The TMS-evoke motor-evoked potentials (MEP) will be measured to determine the use of the ipsilesional corticospinal and the contralesional cortico-reticulospinal tract, with MEP latency serving as the secondary outcome measure. The single or paired-pulse TMS will be applied at the respective hotspots for the elbow flexor muscle, i.e., Biceps Brachii, over the ipsilesional primary motor cortex (from which the corticospinal tract originates) and contralesional premotor cortex (from which the cortico-reticulospinal tract originates) with reference to the impaired arm. A 3 min 20 channel Resting-state EEG will also compute the *brain symmetry index* (BSI) as the third outcome measure for evaluating the acute effect of HD-tDCS on brain plasticity. The BSI is defined as the mean of the absolute value of the difference in the mean hemispheric amplitude spectrum; values range from 0 (no asymmetry, normal control) to 1 (maximal asymmetry, more impaired brain function). The total three assessments will last for ~33 min (10 mins subset FU-UE assessment, ~10 mins TMS MEP, and 3 mins EEG recording plus 10 mins procedure time), which will be within the effective period of HD-tDCS. Baseline measurement will be performed at the beginning of the study on the first visit. To ensure there is no carry-over effect, we will compare the outcomes of pre-stimulation measurement with the baseline for each visit.

All recorded data will be de-identified for the analysis. Identifiers might be removed, and the de-identified information may be used for future research without additional informed consent from the subject.

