## **L. Statistical Analysis Plan**

The statistical and power analysis will be led by [name], Assistant Professor of Research in Department of Biostatistics & Epidemiology, Hudson College of Public Health within the University of Oklahoma Health Sciences Center. The obtained preliminary data will refine our power analysis to provide a more precise estimation of sample size for a future full trial. The effect of HD-tDCS is determined by the change in Fugl-Meyer upper extremity Part A score (primary outcome measure), change in Transcranial Magnetic Stimulation (TMS)-Evoke Motor-evoked Potentials (MEP, secondary outcome measures), and change in Brain Symmetry Index (other outcome measures). All statistical analysis was completed using commercial software Statistical Analysis Systems (9.4, SAS, Carey, NC, USA). After checking for and finding no evidence of a non-normal outcome measure distribution, we analyzed the data using generalized estimating equation (GEE) in SAS using PROC GENMOD. The fixed factors are group (anodal, cathodal, sham), time (pre and post intervention), and their interaction, and the random factor is subject ID. This technique uses correlated linear models for each outcome variable (17,18).

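### The planned group-by-time analysis uses raw pre-to-post change; adjusting for each visit's pre-stimulation value could sharpen the active-versus-sham contrasts at almost no cost

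*Combined protocol and SAP*

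**What the plan says.** Section L (Statistical Analysis Plan) defines the effect as change: "The effect of HD-tDCS is determined by the change in Fugl-Meyer upper extremity Part A score (primary outcome measure". It treats MEP and the Brain Symmetry Index in the same way. On estimation it says "we analyzed the data using generalized estimating equation (GEE) in SAS using PROC GENMOD", and on the model terms: "The fixed factors are group (anodal, cathodal, sham), time (pre and post intervention), and their interaction, and the random factor is subject ID". It names no working correlation structure, no covariate and no visit term.

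Section D (Assessments and Outcome Measures) provides the data: "The following assessments will be performed for baseline, pre- and (immediate) post-intervention time frames". The only other use it states for the pre-stimulation values is a carry-over check: "To ensure there is no carry-over effect, we will compare the outcomes of pre-stimulation measurement with the baseline for each visit". No section provides for adjusting the post-stimulation value for the pre-stimulation value.

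On size, Section A aims to "recruit 12 eligible patients in one year and retain most of them to complete this trial". It also reports, for the later study: "Our pilot power analysis determined that at least 40 stroke patients will be needed in a full R01 trial".

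**The concern.** A change score subtracts the whole pre-stimulation value. That is the most precise choice only if post follows pre one for one within a person. In a cross-over each participant already serves as their own control, so stable differences between people cancel from the active-minus-sham contrast. A high overall pre/post correlation, driven mainly by differences between people, therefore does not justify the change score. What counts is the pre/post correlation left within a visit once the person's own level is removed. If it is well below 1, subtracting the full pre-stimulation value adds noise.

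At stake is the width of the intervals for anodal minus sham (Aim 2a) and cathodal minus sham (Aim 2b), for all three outcomes, in a trial of 12 people.

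**Working it through.** **The plan's own figure.** The 40 participants for the full trial cannot be reproduced, because the documents give no alpha, power, effect size or SD. If one assumes a two-sided 5% test of a paired contrast with 80% power, 40 people correspond to a standardised difference of (1.960 + 0.842)/√40 = 0.44. That is a back-calculation, not a check.

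**Step 1: what the planned model estimates.** Three conditions by two times give six cells, and group, time and their interaction fit a free mean to each. In a simulated complete data set of 12 people, the two GEE interaction coefficients were −0.0624 and 0.0433 under both independence and exchangeable working correlation. The differences in mean change were the same numbers. An autoregressive structure ordered by visit gave a different estimate, so the equality is not general. No such structure estimates a slope on the pre-stimulation value.

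**Step 2: variance of the contrast.** Assume equal variances (set to 1), correlation ρw between pre and post at the same visit, and ρb between any two values from different visits. Define r = (ρw − ρb)/(1 − ρb). For one person, the active-minus-sham difference in post, less b times the difference in pre, has variance

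2(1 − ρb)(1 − 2br + b²).

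- Change (b = 1): the last factor is 2(1 − r).
- Adjusted (b = r, the minimum): 1 − r².
- Post only (b = 0): 1.

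Adjusted over change is (1 − r²)/[2(1 − r)] = (1 + r)/2. When r is below 0.5, 2(1 − r) exceeds 1, so change is less precise than ignoring the pre-stimulation value.

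**Step 3: allow for estimating the slope with 12 people.** There are 36 post values. Subtracting 12 for subjects, 2 for visits and 2 for conditions leaves 20 error degrees of freedom. Estimating the slope inflates the variance by about 1 + 1/(20 − 2) = 1 + 1/18. The simulation used 5,000 trials per row, six balanced orders, and subject and visit terms in both analyses.

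| r | (1+r)/2 | × (1+1/18) | Simulated variance ratio, n = 12 | Simulated CI width ratio, n = 12 |
|---|---|---|---|---|
| 0 | 0.50 | 0.53 | 0.52 | 0.73 |
| 0.5 | 0.75 | 0.79 | 0.79 | 0.89 |
| 0.75 | 0.875 | 0.92 | 0.91 | 0.97 |
| 0.8 | 0.90 | 0.95 | 0.95 | 0.98 |
| 0.9 | 0.95 | 1.00 | 1.00 | 1.00 |

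If one active condition is compared with sham in isolation (11 error degrees of freedom), the inflation is 1 + 1/9, and the gain vanishes near r = 0.8: 0.90 × 1.111 = 1.00.

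**Step 4: the slope must be within-person.** In 400 simulated trials with ρw = 0.95 and ρb = 0.90 (r = 0.5), adding only the raw pre-stimulation value to the GEE gave a variance ratio of about 0.95. Splitting it into the person's mean and the deviation from that mean gave about 0.82. The raw slope is dominated by differences between people and stays close to 1.

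**Step 5: what it could mean for 40.** If 40 had been sized on the change contrast (an assumption), the large-sample equivalent is 40 × (1 + r)/2: 30 at r = 0.5, 35 at r = 0.75 and 38 at r = 0.9.

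**The case against.** The strongest reply is that r may well be high. Pre and post values come from one visit of up to 3 hours, while visits are at least 2 weeks apart. Anything that varies by day, such as the participant's state or the TMS and EEG set-up, is shared by both values and raises r. The documents do not quantify this, but the point stands: from r of about 0.8 upwards there is little to gain at n = 12.

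The second reply is that change has a robustness that adjustment lacks. Carry-over that shifts pre and post at a visit equally cancels from the change score, whereas a slope of r removes only part of it. In simulation, both active conditions carried over by an assumed 1 within-person SD. The change contrast stayed unbiased. The adjusted anodal-minus-sham contrast was biased by about −0.2 SD at r = 0.2 and about −0.14 SD at r = 0.5. At n = 12 its mean squared error was still lower for r up to 0.5, and at most about 8% higher at r of 0.8 to 0.9. At n = 40 it was about 1.2 times that of change at r = 0.2. This is a real trade-off and belongs in the plan, but it is modest at the pilot's size.

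Third, this is a 12-person proof-of-concept study with feasibility as Aim 1, and the change contrast is the effect the plan defines. That is correct, and it limits the consequence to interval width.

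**Conclusion.** The point holds as one of lost precision. The planned contrast is not biased by this choice and its result remains valid. At n = 12 the adjusted variance is between about 0.5 and 1.0 times that of the change analysis, depending on an r that the documents do not give. This rests on complete data, equal pre and post variances, an independence or exchangeable working correlation, and the interaction being the intended test. Section L does not name the test, but defining the effect as change implies it.

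A reader might go further in three ways that the documents do not support:

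- **That r is low because participants are stable between visits.** No section gives a correlation, and stability between visits does not by itself make r low.
- **That the pilot will hand the full trial an inflated variance.** Section L says only that the data will refine the power analysis and names no variance. The change-score variance is the right input for a trial analysed on change. Pre and post values are both kept, so the adjusted variance can be computed later.
- **That a definite gain in power follows.** No alpha, power or effect size is stated, and the calculations above use least squares with visit terms and balanced orders, not the planned GEE. Section D says only that the order is randomised.

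The change is a cheap improvement, not a necessary correction.

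**What to change.** In Section L, model the post-stimulation value of each outcome with condition, visit, that visit's pre-stimulation value, and subject as a fixed effect. Alternatively, keep the GEE and add the person's mean pre-stimulation value as a second covariate. Either form makes the slope within-person; the raw pre-stimulation value alone does not. Report anodal minus sham and cathodal minus sham from this model.

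Keep the change-score contrast as a stated sensitivity analysis. Report the estimated r and the residual variance from both analyses, so that the full trial can be planned on whichever analysis it will use.

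The cost is SAP wording and one degree of freedom for the within-person slope (the GEE form spends one more coefficient on the person's mean). It needs no new data and no added participant burden. The plan should also say that adjustment protects less than change when carry-over shifts pre and post equally, and that the result will be read alongside the carry-over check in Section D.

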## **M. Data and Safety Monitoring Plan**

*Overall framework for safety monitoring and what information will be monitored.*

The PIs will be responsible for ensuring participants' safety on a daily basis due to the low risk of this mechanistic clinical trial study. All reportable new information (safety data) will be reported to the IRB within 5 days per University policy by the PI following a review with the study team and DSMB. These include but are not limited to new or increased risks, adverse events, serious adverse events, non-compliance with IRB policy, researcher error/protocol violation, and unresolved participant complaints.

Research data will be monitored for completeness every week. The RedCap™ (Research Data Capture) system will be utilized to store all patient demographic information (coded), clinical assessment scores, and all processed data via encrypted university computers. The raw/unprocessed data be coded with a unique patient identifier and stored offline on an encrypted and password protected laboratory computer and backed up to secure online storage through the Shared Services File Storage Service managed by OU/OUHSC IT. Raw data on the computer cluster will be accessible only to study investigators.

*Frequency of monitoring plans for interim analysis and stopping rules.*

A monthly summary of reportable new information (safety data) will be made by the Clinical Research Coordinator (covered by the subcontract to OUHSC), in collaboration with team members in the project and then reviewed by the PIs. Raw research data will be reviewed weekly by the study investigators for organization, completeness, and confirmation of backup. Data quality issues, if any, will be discussed with the investigators and recommendations will be made for immediate solutions by the investigators. An interim analysis will be conducted on research data and directly available to the Program Officer on request. Due to the low risk of the proposed study, minimal adverse events are expected, and no 'a priori' stopping rules will be assigned.

***Management and reporting of adverse events and serious adverse events.***

Upon first knowledge of an adverse event or serious adverse event (also including any reportable new information), the event will be reported to the clinical research coordinator. After reviewing with the PIs, the OUHSC clinical research team, and relevant personnel, the clinical research coordinator will generate the IRB report and queue for review and submission by the PI to the IRB within 5 days per University/IRB policy. A copy will also be sent to the Office of HRPP. The study PI will report all adverse and serious adverse events to the NIH within the same time frame. The PI will have weekly meetings with team members to review all reportable new information.

***Individual responsible for study monitoring***

Overall study monitoring will be the responsibility of the study doctor and PI. The study doctor and PI will utilize a clinical research coordinator to prepare safety and data monitoring reports as required.

**N. Data Sharing**

We are committed to enhancing the value of research and furthering the advancement of public knowledge. We recognize that the public dissemination of our scientific results can facilitate the creation of collaborative efforts with domestic and international collaborators. Furthermore, we recognize that the proposed project may result in novel ideas for new methods, technologies, and data that could benefit the entire research community. Therefore, final research data will be shared openly and timely in accordance with the most recent NIH guidelines ([http://grants.nih.gov/grants/policy/data\\_sharing/](http://grants.nih.gov/grants/policy/data_sharing/)) while being mindful that the confidentiality and privacy of participants in research must be protected at all times.

More specifically, sharing of data and resources generated by this project is an essential part of our proposed activities and will be carried out in several different ways including presentations at national scientific meetings, and publications in peer-reviewed journals. We wish to make our results available to the community of scientists interested in stroke rehabilitation and to help avoid unintentional duplication of research. All research data obtained at this study will be shared with members in our interdisciplinary team across the University of Oklahoma (OU) and OU Health Sciences Center (OUHSC). We welcome collaboration with others (outside our team) who can fruitfully use and apply the rehabilitation plan we developed in this pilot trial and following R01 study. The research team shall create and maintain a database to integrate de-identified clinical assessment results and acquired EEG, EMG, behavior data, in order to facilitate data sharing. The database shall be accessed through a secured web portal. All investigators at this project will employ best practice implementations for accessing the data via institute-owned, encrypted computers to increase the security of the network and to assure the availability, integrity, and confidentiality of information. Any data distributed to additional potential research collaborators outside of this project will be de-identified prior to sharing to preserve the confidentiality of the participants' identity to protect Human Subject Privacy.

The results of this pilot trial will be disseminated through ClinicalTrials.gov, in accordance with institutional policies that ensure compliance with NIH policies on clinical trial registration and reporting. The results of the study will also be disseminated through publications and presentations at national/international meetings, and discussed at local seminars. The PI [name] together with clinician investigator Co-PI [name] will be responsible for handling ClinicalTrials.gov requirements for this project. The trial will be registered with ClinicalTrials.gov prior to enrolling in the first subject. Once a record is established, [name] and [name] will confirm the accuracy of record content; resolve problems; maintain records including content updates and modifications; and aggregate results reporting at the conclusion of the project and adverse event reporting (if any). All reporting and submission of results will occur within the timeframes in the NIH Policy on Dissemination of NIH-Funded Clinical Trial Information. Informed consent documents for this clinical trial will include a specific statement relating to the posting of this trial's information and results at ClinicalTrials.gov.

We will make available final research data when findings from our study are accepted for publication, as recommended in NIH guidelines on data sharing. While there will be no restrictions on access, the distribution of final research data will be strictly controlled and documented based on university policies and the NIH Principles and Guidelines document. Data requests will require registration, including a valid email address. The PI will issue (by email) to each requestor a password that will allow access to a cloud-based download page, and data will be downloaded over an encrypted (SSL2) connection. We will make all analysis tools, algorithms, software interfaces, source codes and documentation, modeling tools, and other software technologies developed and/or enhanced during the project freely available to the scientific community with an open-source license through the lab website. If any source code is developed in the course of analyzing the data collected in the study, we will also deposit source code in open-source libraries. Should any intellectual property arise which requires a patent, we will ensure that the technology (materials and data) remains widely available to the research community in accordance with university policies and the NIH Principles and Guidelines document. In general, we expect the data will be available through speaking engagements and publications, presentations at scientific symposia and seminars. The effort will be made to publish our research findings in scientific journals.

All published work will likely be presented in abstract form at relevant international conferences of the American Society of Neurorehabilitation, Society for Neuroscience, American Heart/Stroke Association, American Physical Therapy Association, American Congress of Rehabilitation Medicine, etc.

#### **O. Confidentiality**

OUHSC RedCap™ (Research Data Capture) system will be utilized for the storage of all patient demographic information (coded), clinical assessment scores, and all processed data via encrypted university computers. The raw/unprocessed data be coded with a unique patient identifier and stored offline on an encrypted and password protected laboratory computer and backed up to secure online storage through the Shared Services File Storage Service managed by OU/OUHSC. Raw data on the computer cluster will be accessible only to study investigators.

All recorded experimental data (including videos) will be de-identified before the analysis. The database shall be accessed through a secure web portal. All investigators employ best practice implementations for personal computers to increase the security of the network and to assure the availability, integrity, and confidentiality of information. Any data distributed to additional potential research collaborators outside of the study team will be de-identified prior to sharing to preserve the confidentiality of the participants' identity.

With written permission from the subjects, video recordings may be performed using a regular camera. The videos will be used to detect the abnormal movement patterns from the stroke subjects to aid with data analysis. All videos will be de-identified by adding a face cover to the subject's image. However, it may not be destroyed after the study since the result from video analysis may be a part of our publications. The videos as the original data will be saved in an encrypted and password protected laboratory computer and backed up to secure online storage through the Shared Services File Storage Service managed by OU /OUHSC IT.

